6.1.1 Amendment (05/04/2012)

All patients when enrolled should have a sample of blood taken for storage/serology if they consent to having extra blood samples taken. If the patient is later shown to have HSV meningitis this can be used to test for type specificity. If they have another diagnosis the sample can be stored if the patient has consented to having their samples stored and used in the future.

6.1.2 Substantial Amendment 12 (03/09/2013)

All patients will consent to gifting any leftover samples (blood and CSF) to the University of Liverpool for further work on diagnostics.

6.2 Summary of Investigations

		All patients	Controls	Aseptic Meningitis	HSV Meningitis	Suspected BM
Sample	Test					
CSF	Opening Pressure	X				
	Microscopy and Culture	X				
	Protein	X				
	Glucose	X				
	CSF Viral PCR panel			x		
	Meningococcal/ Pneumococcal PCR +/- 16S PCR					X (If microscopy /culture negative.)(according to local protocol)
	4.5ml CSF for genomics	X (if consented to)				
3-5ml CSF for DNA sampling	X(if consented to)					
Blood	FBC	X				
	Clotting	X				
	U and E's	X				
	LFTs	X				
	CRP	X				
	Glucose	X				
	Blood Cultures	X				
	Serology	X				
	HSV type specific serology				X	
	HIV serology			X	X	X
HSV type specific serology (at 6 months).				X (If initial type specific serology negative)		
4.5ml EDTA blood for proteomics (SST)	X (if consented to)					
18.5ml for genomics	X(if consented to)					
18ml for DNA sampling	X(if consented to)					
Throat swab	Enterovirus PCR			X		
Stool/rectal swab	Enterovirus PCR			X		
Lesions (oral, skin, genital)	HSV PCR, VZV PCR			X		
Vesicle Fluid (if present)	HSV, VZV, enterovirus and parechovirus PCR			X		
Self taken genital swab (see text)	HSV PCR			X	X	

 Samples to be taken over and above what would be routine practice.

All samples may be stored (if consented to), anonymously, for future research studies.

6.3 Schedule for Follow-up

6.3.1 Primary Acute Outcomes

6.3.1.1 Time to fever resolution

Temperature will be assessed 6 hourly for the first 48 hours, and thereafter 12 hourly (unless it is clinically necessary to do more frequently). Time to fever resolution will be recorded in days, (temp <37.5 for > 24 hours) for patients febrile on or after admission. (This will be recorded as the time between admission and the first temperature of <37.5 – after which the temperature remained less than 37.5 for > 24 hours.)

6.3.1.2 Resolution of Acute Morbidity

The Total Morbidity Score (TMS) (see below) will be assessed daily until a participant has a score of 0 for seven consecutive days. This score has been used on viral meningitis previously (19), and ranges from 0 to 21. Resolution of acute morbidity (using the TMS) including time to first symptom score of zero, and time to headache score of 0, has been used in previous studies of viral meningitis (19, 20).

The Total Morbidity Score. *This is the sum of the scores for the following six individual symptoms: headache, nuchal rigidity, photophobia, myalgia, fever, and nausea/vomiting. Each symptom/sign, other than headache, is ranked by the subject on a four-point scale (0=absent and 3=severe). Headache is ranked on a seven-point scale (0-6). It, therefore has a range from 0-27. This self-completed questionnaire takes less than five minutes to complete.*

In current hospital practice, many patients with meningitis are discharged before these symptoms are completely resolved. For these patients assessment will continue at home. Participants will be given a thermometer and asked to record their oral temperature daily and their TMS on a pre-prepared form. They will be given a postage paid envelope to return the data (anonymously).

Patients will be contacted by a member of the study team to ensure the forms are completed and returned after 21 days.

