6.3.1.4 Clinical Relapse

Clinical Relapse will be defined as

- A recurrence of fever, after fever resolution, with no other cause found. Fever is defined as one recording above 38.5 or 2 consecutive readings >38 (at least one hour apart)
- A recurrence of headache (with a score of 3 or more on the TMS) following resolution accompanied by at least one other score of >0 for 2 or more consecutive days.(19)

Clinical relapse will be defined within the first 3 weeks following admission to hospital.

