6.7 Schedule

	Who?	Baseline	Post LP	Daily for 3 weeks from admission	6 weeks (+/- 1 week)	12 weeks (+/- 1 week)	24 weeks (+/- 1 week)	48 weeks (+/- 1 week)
Consent Form	LC/RN	X						
Assessment of eligibility criteria	LC/RN	X						
Review of medical history	RN	X						
Ask re oral/genital ulcers (if not documented in medical history)	RN	X						
Check routine bloods taken (FBC, clotting, U and E's, LFTs, CRP, glucose, blood cultures)*,	RN	X						
Throat Swab for enterovirus PCR	CT							
Blood for proteomics and genomics (SST and PAXgene™ tube to be supplied by BIUK)	CT/RN	X						
Stool sample for enterovirus PCR	CT/RN	X						
If oral/genital/skin lesions present. Swab of oral/genital/skin lesion for HSV/VZV PCR Any vesicles present should have fluid sent for HSV, VZV, enterovirus and parechovirus PCR	CT	(X)						
Lumbar puncture***	CT	X						
If no self reported/documentated genital lesions. Self taken genital swab for HSV if CSF positive for HSV. Women – vulval, vaginal and perianal swab. Men – perianal and penile skin swab.	RN/Patient		(X)					
Meningitest performed	RN/RF		X					
Charlson Index	RN/RF	X						
TMS	Patient/RN/RF			X				
HIT	RN/RF				X	X	X	X
ABNAS	RN/RF				X	X	X	X
EQ5D	RN/RF				X	X	X	X
SF36	RN/RF				X	X	X	X

(X) If appropriate

* If not performed already these should be taken

** One for HSV type specific serology if needed and one for proteomics and genomics work

***Opening pressure, protein, glucose, cell count, microscopy and culture, PCR as appropriate for cell count/clinical judgement, stored

sample for proteomics/genomics. LC= Local collaborator, CT= Clinical team, RN = Research Nurse, RF= Research Fellow

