13 FINANCIAL ARRANGEMENTS

The main study is funded by the Meningitis Research Foundation. Some of the substudies (biomarkers of infection and DNA sampling) have been funded by means of flexibility and sustainability funding. Further funding will be sought for the other substudies.

Funding for substudies 6.9.1-6.9.3 (substantial amendment 12) has been granted from the National Institute for Health Research.

There will be no payments to patients or clinicians.

Thermometers will be provided for patients who are discharged before 3 weeks. Postage paid envelopes will be provided for patients to return the daily temperatures, TMS and questionnaires.

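### The daily TMS has two conflicting end points: stopping after seven zero days leaves part of the 3-week relapse window unscored, while stopping at 3 weeks censors late resolvers

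*Protocol*

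**What the plan says.** Section 6.3.1.2 of the protocol says the TMS "will be assessed daily until a participant has a score of 0 for seven consecutive days". It sets no calendar limit.

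Three other places work to 3 weeks:
- The section 6.7 schedule marks the TMS only in the column "Daily for 3 weeks from admission".
- The end of section 6.3.1.2 has the study team contact patients "to ensure the forms are completed and returned after 21 days".
- Section 13 states "Thermometers will be provided for patients who are discharged before 3 weeks".

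The TMS feeds several secondary outcomes in section 7.1.2:
- **Resolution of acute morbidity.** Section 6.3.1.2 names the time to the first zero symptom score and the time to a zero headache score. Section 7.3 plans a log-rank comparison.
- **Relapse.** Section 6.3.1.4 has a headache criterion, "A recurrence of headache (with a score of 3 or more on the TMS) following resolution", which must be accompanied by another non-zero score, and a temperature criterion, "A recurrence of fever, after fever resolution, with no other cause found". On timing: "Clinical relapse will be defined within the first 3 weeks following admission to hospital".
- **Recurrence.** Section 6.3.2 counts an episode only if it comes four weeks or more after the TMS has reached 0.

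Sections 1.1 and 6.4.6 end the TMS for patients newly enrolled from May 2015.

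**The concern.** The two rules produce different data. The seven-zeros rule follows a patient through to resolution, but it can end before the relapse window closes. The 3-week rule covers the relapse window, but it can end before resolution. A site that follows the text and a site that follows the schedule will hold different days of data for the same kind of patient. No later analysis can recover days that were never scored.

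The protocol intends to compare outcomes between viral meningitis, bacterial meningitis and controls. If these groups resolve at different speeds and unscored days are counted as relapse-free, the group that resolves faster can appear to relapse less simply because a larger part of its window was not recorded. The results are also meant to inform the design of a later treatment study.

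**Working it through.** The protocol states no figure to reproduce here, so the check is day arithmetic on its own definitions. Let d be the first day with a TMS of 0, counted from admission, and let the relapse window close on day 21.

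**Seven-zeros rule (6.3.1.2), scores staying at 0**
- Last scored day = d + 6.
- Unscored days left in the window = 21 − (d + 6) = 15 − d, or 0 if d is 15 or more.
- Post-zero days in the window = 21 − d.

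The protocol gives no resolution times, so the values of d are assumptions:

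| Assumed d | Last scored day | Unscored days | Post-zero days | Share unscored |
|---|---|---|---|---|
| 4 | 10 | 11 | 17 | 65% |
| 7 | 13 | 8 | 14 | 57% |
| 10 | 16 | 5 | 11 | 45% |
| 14 | 20 | 1 | 7 | 14% |
| 15 | 21 | 0 | 6 | 0% |

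The gap affects every patient first at 0 by day 14. The post-zero time actually watched is (d + 6) − d = 6 days for every d up to 15. What varies with d is the share of the window that goes unscored.

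**3-week rule (6.7)**
- The last scored day is 21, so no relapse-window day is lost.
- A first zero on any day up to 21 is recorded. On days 16 to 21 it cannot be followed by six more scored zeros, because 16 + 6 = 22.
- A first zero after day 21 is not recorded. Resolution is censored at day 21, and the recurrence clock in 6.3.2 has no recorded start.

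To show the possible size of the last group, assume exponential resolution times. The share unresolved at day 21 is then 0.5^(21/median). Assumed medians of 5, 7, 10, 14 and 21 days give about 5%, 12.5%, 23%, 35% and 50%. Section 6.3.1.2 says only that many patients go home with symptoms still present.

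**Combining the rules**
- Stopping at whichever comes first keeps both gaps.
- Stopping at whichever comes later removes both: no relapse-window day is unscored, and the schedule cuts off no resolution date.

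**The case against.** Several points against the concern carry weight.

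- **Most of the document points to 3 weeks.** The schedule, the form return and the thermometers all agree, and nothing shows that any site stopped early. If 3 weeks was the working rule, the relapse gap did not arise. The text of 6.3.1.2 still says otherwise, and nothing makes the schedule prevail.
- **Fast resolvers are not watched for less time.** A reader might infer that they are. The arithmetic does not support it: post-zero time under the seven-zeros rule is 6 days for every d up to 15, and shorter after that because the window closes. Fast resolvers lose the largest share of the window.
- **First zeros on days 16 to 21 are not lost.** A reader might infer that they are, since seven zeros cannot be completed by day 21. Section 6.3.1.2 describes resolution by the first zero score; the seven days are a rule for stopping collection.
- **The day-21 cut does not by itself bias the log-rank test.** It is administrative right-censoring, which that test handles. The loss is of late resolution dates, of the median in a group with half or more unresolved, and of the recurrence start.
- **The data can be pooled for resolution.** Any first zero by day 21 is recorded alike under both rules, so censoring at day 21 makes them comparable. Relapse data are not comparable unless the rule applied is known.
- **The post-zero shares are approximate.** The relapse criteria run from headache or fever resolution, which may precede a total score of 0. The fever criterion uses temperature, not the TMS. At home, though, temperature is recorded along with the TMS and may stop with it; the protocol does not say. Patients are asked to report readmission, but that catches only relapses that lead to one.
- **Collection has ended for new patients.** The stop date was May 2015 and the current version is dated November 2015, so extra diary days cannot be added for the earlier cohort. This limits the remedy for existing data and leaves the contradiction in place.

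**Conclusion.** The concern holds in a limited form. Sections 6.3.1.2 and 6.7 give different end points for the daily TMS, and the protocol does not reconcile them.

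Followed literally, 6.3.1.2 leaves 15 − d days of the 3-week window unscored for a patient first at 0 on day d, up to d = 14, who stays at 0 until scoring stops. That undercounts TMS-based headache relapse, proportionately most where resolution is fastest. Following 6.7 covers the window, but censors resolution at day 21 and leaves the recurrence clock without a recorded start in patients still above 0.

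The 15 − d result follows from the protocol's definitions alone. The percentages rest on assumed values of d, and the unresolved shares rest on assumed exponential medians. The documents do not show which rule sites used, so the actual undercount cannot be stated. Only secondary outcomes are touched; the primary outcome, prevalence, is not.

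**What to change.** **Protocol text, and any reuse of this schedule.** Give one rule in both 6.3.1.2 and 6.7: daily TMS and temperature to at least day 21 from admission whatever the score, continuing past day 21 only until seven consecutive zeros are reached. Align the form-return wording with it. Post-zero time within the window will still vary as 21 − d, because 6.3.1.4 anchors the window to admission, but no day of it will go unscored.

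**Data already collected.**
- State which rule was applied, by site if it differed.
- Report relapse against the days actually observed, and do not count unscored days as relapse-free.
- Take resolution as the first TMS of 0, censored at the last entry.
- Report how many patients have no recorded start for the recurrence clock.

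**Cost.** For existing data, a wording change and a short analysis rule. Where the schedule is used again, early resolvers would complete 15 − d more daily forms (11 for an assumed d of 4), each taking under five minutes by the protocol's own estimate. Late resolvers would need a second sheet.

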6.3.1.3 Morbidity index

In addition to the TMS we will also assess the co-morbidity of the participants using the Charlson Index(21) which has been validated previously and uses a scoring system to predict 10 year survival. This will help us compare outcomes with regard to co-morbidities.

6.3.1.4 Clinical Relapse

Clinical Relapse will be defined as

- A recurrence of fever, after fever resolution, with no other cause found. Fever is defined as one recording above 38.5 or 2 consecutive readings >38 (at least one hour apart)
- A recurrence of headache (with a score of 3 or more on the TMS) following resolution accompanied by at least one other score of >0 for 2 or more consecutive days.(19)

Clinical relapse will be defined within the first 3 weeks following admission to hospital.

6.3.2 Recurrence

Recurrence of viral meningitis will be defined as a recurrence of clinical symptoms, with CSF pleocytosis at least four weeks after complete symptom resolution (i.e. a TMS of 0).

Participants will be asked to contact the research team if they are readmitted to hospital with similar symptoms after they are discharged from hospital.

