6.4.2 Headache Impact Test (HIT)™

This will be used to assess the impact headaches have on a person's ability to function on the job, at home, at school and in social situations. This tool which is particularly suitable for assessing the long term morbidity, has been developed for migraine and chronic headache (<http://www.headachetest.com/>) (23). We will compare between the groups of patients with viral meningitis and other types of meningitis. If there is a significant group of patients with migraine then they will also be used as a comparator group. Post LP headache will be defined as either a) new onset headache or b) worsening of headache following lumbar puncture which is worse on being vertical and eased on lying down with no other cause found.

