6.4.6 Substantial Amendment 17 (01/05/2015)

Some patients will be sent an additional questionnaire 2 years after discharge to monitor the significant differences observed at the 48 week time point. From May 2015, the TMS and follow-up questionnaires will no longer be given, or sent, to new patients enrolled on the study.

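### Relapse and recurrence cannot be ascertained completely or consistently as defined: the headache arm does not exclude post-LP headache, the TMS is withdrawn or stops early, and some episodes fit neither rule

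*Protocol*

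**What the plan says.** - **Relapse window (6.3.1.4).** "Clinical relapse will be defined within the first 3 weeks following admission to hospital".
- **Relapse, fever arm (6.3.1.4).** "A recurrence of fever, after fever resolution, with no other cause found".
- **Relapse, headache arm (6.3.1.4).** "A recurrence of headache (with a score of 3 or more on the TMS) following resolution accompanied by at least one other score" above zero, for at least two days running. No other-cause condition is attached.
- **Recurrence (6.3.2).** "Recurrence of viral meningitis will be defined as a recurrence of clinical symptoms, with CSF pleocytosis at least four weeks after complete symptom resolution", where resolution is spelled out as a TMS of 0. Patients are asked to tell the research team if they are readmitted with similar symptoms.
- **Post-LP headache (6.4.2).** Defined under the Headache Impact Test (HIT) as a new headache or "worsening of headache following lumbar puncture which is worse on being vertical and eased on lying down with no other cause found". The relapse rule does not refer to it.
- **TMS recording.** Section 6.3.1.2 says the score "will be assessed daily until a participant has a score of 0 for seven consecutive days". The schedule in 6.7 has it every day through the first three weeks from admission.
- **Amendment 17 (1.1 and 6.4.6).** "From May 2015, the TMS and follow-up questionnaires will no longer be given, or sent, to new patients enrolled on the study". Section 13.1.1 also withdraws the home thermometers and return envelopes.
- **Outcome (7.1.2, item c).** Incidence of relapse and recurrence is listed without an expected value or a stated population.

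**The concern.** The protocol itself fixes both event definitions, so this is not detail left to an analysis plan. Four features of the current text decide which episodes can be counted.

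1. The headache arm does not separate a return of meningitis symptoms from a headache caused by the lumbar puncture, which most participants have.
2. Recurrence and headache relapse both need a TMS that patients enrolled from May 2015 do not receive. Sections 6.3.1.4, 6.3.2, 6.7 and 7.1.2 were left as they were.
3. Two sections give different end points for TMS recording, and one of them ends before the relapse window does.
4. The relapse and recurrence windows start from different events and do not meet.

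Recurrences in viral meningitis are a named secondary objective, and the study's data are meant to inform the design of a phase III trial. If these rules are applied as they stand, the counts will depend on when a patient was enrolled, which section the site followed and how fast the patient recovered.

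**Working it through.** The protocol gives no expected or observed incidence, so there is no figure to reproduce. The check is date arithmetic plus a comparison of sections.

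**1. Headache arm.** Three conditions must hold: headache has resolved; it returns with a score of 3 or more; another item scores above zero for two or more consecutive days. The fever arm adds that no other cause was found; the headache arm does not. A post-LP headache under 6.4.2 that meets all three is therefore a relapse as written. The HIT, where the post-LP definition sits, is first given at 6 weeks (6.7), after the relapse window has closed.

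**2. Enrolments from May 2015.**
- Recurrence requires a prior TMS of 0. No TMS means no recorded zero and no date from which to count four weeks.
- Headache relapse is scored on the TMS, so it cannot be scored.
- Fever relapse does not use the TMS, but 13.1.1 removes the home thermometers. Section 6.3.1.2 says many patients leave hospital before symptoms have fully resolved, so part of the window can fall after discharge.
- Section 13.1.1 describes the decision as stopping the TMS at discharge. Read that way, an in-hospital score might survive, but nothing after discharge would.

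The share of patients affected is not given. Assuming uniform enrolment, the share of calendar time after 1 May 2015 is:

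| Assumed enrolment period | Days after 1 May 2015 / total days | Share |
|---|---|---|
| 28/06/2011 to 31/12/2015 | 244 / 1647 | 15% |
| 28/06/2011 to 01/10/2016 | 519 / 1922 | 27% |
| 03/09/2013 to 01/10/2016 | 519 / 1124 | 46% |

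The start dates are those of version 1 and of the version 6 expansion (section 16); the end dates are the two extensions in 6.6. Actual first and last enrolment dates are not in the document.

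**3. When recording stops.** Number the relapse days 1 to 21. Under 6.3.1.2, a patient at zero on days 5 to 11 has seven consecutive zeros and stops. Days 12 to 21 are unrecorded: 21 − 11 = 10 of 21 days. Under 6.7 they are recorded. Conversely, if recording ends at day 21 as in 6.7, a patient still scoring above zero then has no recorded zero from which to date a later recurrence.

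**4. Gap between windows.** Relapse closes on day 21 from admission. With first TMS 0 on day R, recurrence opens on day R+28. Days 22 to R+27 belong to neither, a length of (R+27) − 22 + 1 = R+6 days.

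| R | Days in neither window | Length |
|---|---|---|
| 3 | 22–30 | 9 |
| 7 | 22–34 | 13 |
| 14 | 22–41 | 20 |
| 21 | 22–48 | 27 |

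The gap lengthens with slower recovery. An episode inside it is uncounted even with CSF pleocytosis.

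**The case against.** **The windows need not meet.** Relapse is a return of acute fever or headache without CSF confirmation; its headache criterion cites an earlier study of enteroviral meningitis. Recurrence is a new episode with CSF pleocytosis. An interval between them is an ordinary way to avoid relabelling one illness as two. This stands as an argument against forcing the windows together: a longer relapse window would run past the scheduled TMS, where headache relapse could not be scored. It does not justify leaving a CSF-confirmed episode in the interval with no category.

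**Post-LP headache is not simply counted as relapse.** A reader might infer that it is. The rule requires prior resolution, the score threshold and a second symptom for two or more days. Headache that worsens after the puncture without having resolved does not qualify. This stands: the defect is a missing exclusion, not automatic inclusion. Controls also had a lumbar puncture and the same follow-up, so the effect can appear in the comparison group too; that does not remove it from the incidence in either group.

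**Later enrolments are not invisible.** A reader might infer that no relapse or recurrence can be found in them. Self-report on readmission survives Amendment 17, and the fever arm needs no TMS. This stands, but readmission reveals an episode without supplying the TMS 0 that the definition asks for.

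**A persisting symptom need not bar recurrence for good.** The rule asks for a TMS of 0, not a sustained one, so a single zero day satisfies it. This stands.

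**The denominator may be set elsewhere.** Section 7.1.2 names none, and an analysis plan not shown here may restrict it. This stands as a caveat; within the protocol nothing limits outcome (c) to patients with a TMS.

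**Conclusion.** The point holds as a defect of ascertainment. Under the current text, outcome (c) cannot be established completely or in the same way for all patients. The sizes that can be given are 10 of 21 relapse days unrecorded in the worked example under 6.3.1.2, and R+6 unclassified days for each patient (13 for R = 7, 20 for R = 14). The number of patients without a TMS is unknown; the calendar shares of 15% to 46% rest on assumed dates and uniform enrolment.

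It would be tempting to conclude that the reported incidence is wrong, or that relapse is inflated. The document does not support either. It states no incidence. An unexcluded post-LP headache would add events, while stopped recording, a missing TMS and the gap would lose them. Neither the direction nor the size of the net bias can be computed. The changes are worth making because they are specific, inexpensive and alter what is counted, but they concern one of ten listed secondary outcomes and leave the primary outcome untouched.

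**What to change.** 1. **Section 6.3.1.4, headache arm.** Add that no other cause was found and that the headache does not meet the post-LP definition in 6.4.2.
2. **Sections 6.3.1.2 and 6.7.** Reconcile them so that TMS recording covers the whole three-week relapse window, whatever the run of zeros.
3. **Patients without a TMS.** Limit TMS-based relapse to patients and days with a recorded score. For recurrence, either restrict it to patients with a TMS or, for those enrolled from May 2015, let complete symptom resolution be documented by history. Report recurrence per person-time. Update 6.3.1.4, 6.3.2, 6.7 and 7.1.2 to match Amendment 17.
4. **The interval.** Keep both windows, and report CSF-confirmed episodes from day 22 to day R+27 as a separate named category.

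The cost is mainly wording, plus taking a history of resolution if that option is chosen. The downsides are small differences from the relapse definition in the cited study and a smaller denominator for the TMS-based outcomes.

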6.3.3 Longer term outcomes

Longer term exploratory analyses will be conducted on the HIT, SF-36 and ABNAS (see below) to assess their suitability as outcome measures in future studies of viral meningitis. The SF-36 and ABNAS will be compared with published normative data. [name] from the Walton Centre, who is an expert on validation and implementation of rating scores will provide advice on evaluation of the different scores.

Patients will also be asked to document if they have had any episodes of genital lesions throughout the follow-up period. All patients will be asked and this will enable us to compare the rate of genital recurrence in those patients with HSV-2 meningitis with the other groups of meningitis and controls. A separate questionnaire will be sent to record this to be returned anonymously with the other questionnaires.

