6.4.5 Amendment 09 (17/09/2012)

Early analysis has shown that there is no difference between the control patients and the viral meningitis patients (n=20 in each group). Therefore, it is postulated that as our control patients are patients that have been hospitalised a more 'healthy' control group is needed. Therefore, we will ask the participants when they are filling in the questionnaires to also give a pack of questionnaires to a relative/friend/neighbour to also fill in and return. Data on age and gender will be collected on these healthy controls.

The HIT, SF-36, ABNAS, and EQ-5D will be performed at 6, 12, 24 and 48 weeks after discharge. Each of these is a patient self-completed questionnaire which collectively will take twenty to thirty minutes to complete. It is important to obtain these serial evaluations so that we can determine the best endpoint for the subsequent treatment study.

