7.1.2 Secondary

- a. Time to fever resolution
- b. Resolution of acute morbidity (using the TMS)
- c. Incidence of relapse and recurrence
- d. Change in Headache Impact Test over the study period
- e. Quality of Life Assessment (SF36)
- f. Neuropsychological Outcome (ABNAS)
- g. Economic Analyses (EQ5D)
- h. To determine the number of people with aseptic meningitis being offered an HIV test and the proportion of these that are positive.
- i. Pathogen Specific Outcomes
- j. Clinical Predictors of outcome or pathogen.

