8.5 Responsibilities – Investigator

The local investigator is responsible for reporting all AEs that are observed or reported during the study, regardless of their relationship to study.

All SAEs must be reported immediately by the investigator to the BIUK coordinating centre on an AE form unless the SAE is specified in the protocol as not requiring immediate reporting. All other adverse events should be reported on the regular progress/follow-up reports.

Minimum information required for reporting:

- Study identifier
- Study centre
- Subject ID
- A description of the event
- Date of onset
- Current status
- The reason why the event is classified as serious
- Investigator assessment of the association between the event and study treatment

- i. The AE form should be completed by a designated investigator, a physician named on the delegation log.
- ii. When submitting an SAE to the BIUK, study sites should also telephone the study manager/data manager on [contact]** to advise that an SAE report has been submitted.
- iii. Send the AE form by fax (within 24 hours or next working day) to the BIUK coordinating centre:

[contact]

- iv. The responsible investigator must notify their R&D department of the event (as per standard local governance procedures).
- v. In the case of a non-fatal SAE the subject must be followed-up until clinical recovery is or until the event has stabilised.

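### Recurrence is found only if the participant reports a readmission, and from May 2015 the TMS-based relapse and recurrence definitions cannot be applied to new patients after discharge

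*Protocol*

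**What the plan says.** Section 7.1.2(c) lists "Incidence of relapse and recurrence" as a secondary outcome.

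Section 6.3.2 defines recurrence of viral meningitis as a return of clinical symptoms "with CSF pleocytosis at least four weeks after complete symptom resolution (i.e. a TMS of 0"). It gives one route of detection: "Participants will be asked to contact the research team if they are readmitted to hospital with similar symptoms after they are discharged from hospital".

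Section 6.3.1.4 defines relapse within three weeks of admission. There is a fever criterion, and a headache criterion that needs a TMS headache score of at least 3 together with another non-zero score.

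Scheduled contact after discharge is set in 6.4.5: "The HIT, SF-36, ABNAS, and EQ-5D will be performed at 6, 12, 24 and 48 weeks after discharge". A genital-lesion form goes with the packs (6.3.3): "Patients will also be asked to document if they have had any episodes of genital lesions throughout the follow-up period". Sections 6.4.3.2 and 6.5.1 add a socio-economic questionnaire, a time-off-work question, and calls at 6 weeks and one year to patients who have not responded.

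Section 6.4.6 then says: "From May 2015, the TMS and follow-up questionnaires will no longer be given, or sent, to new patients enrolled on the study". It also provides a questionnaire at two years for some patients. Section 13.1.1 withdraws the home thermometers and reply envelopes that went with the TMS.

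**The concern.** There are two separate problems.

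The first is detection. The background (2.1) names recurrent HSV-2 meningitis as one of the open questions behind the study, and the outcome data are meant to inform a phase III design. An event that is counted only when a former inpatient remembers to get in touch will be missed some of the time. Every missed event lowers the reported incidence.

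The second is definition. A case definition needs its inputs to be collected. For patients enrolled from May 2015, the score that marks complete resolution and the score that marks headache relapse are no longer collected at home. Section 16.13 says version 7.2 incorporates amendment 17, so the unchanged definitions and the withdrawn instrument stand side by side in the current text. If relapse and recurrence are tabulated without saying who could be assessed, a patient with no data is indistinguishable from a patient with no event.

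**Working it through.** The protocol states no expected rate, precision or sample size for recurrence or relapse, so there is no figure to reproduce. The check sets the sections side by side.

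**Detection of recurrence after discharge**

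| Contact | Section | Described as asking about readmission or repeat lumbar puncture? |
|---|---|---|
| Participant contacts the team | 6.3.2 | Yes, but passive |
| Study-team contact about the 21-day TMS forms | 6.3.1.2 | No |
| HIT, SF-36, ABNAS, EQ-5D at 6, 12, 24, 48 weeks | 6.4.5, 6.7 | No |
| Genital-lesion form | 6.3.3 | No |
| Socio-economic questionnaire, time off work | 6.4.3.2, 6.5.1 | No |
| Calls to non-responders, 6 weeks and one year | 6.5.1 | No; they collect questionnaire answers |
| Six-month serology in some HSV patients | 6.1 | No |
| Three- and 12-month samples in some patients | 6.8.3 | No |

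The schedule in 6.7 has no recurrence row. Genital lesions are asked of all patients so that groups can be compared; recurrence has no equivalent question.

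Size: reported incidence = true incidence × s, where s is the share of recurrences that participants report. The documents give no value for s. For illustration only:
- s = 0.9: 10% of recurrences lost
- s = 0.7: 30% lost
- s = 0.5: 50% lost

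**Definitions against data collected from May 2015**

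| Element | Needs | Post-discharge source for new patients |
|---|---|---|
| Recurrence (6.3.2) | date of TMS 0 | none |
| Headache relapse (6.3.1.4) | TMS headache score of 3 or more | none |
| Fever relapse (6.3.1.4) | temperature readings, no TMS | home thermometer withdrawn |

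Section 6.3.1.2 notes that many patients go home before their symptoms have fully resolved, so the date of TMS 0 will often fall after discharge.

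**How much of the study this touches**

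1 May 2015 (6.4.6) to 1 October 2016 (6.6.2) is 17 months. Against the five-year duration in section 1, 17/60 = 28% of calendar time. This equals the share of patients only if enrolment was even and ran to the end date, which the protocol does not say.

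**What contacts were left at version 7.2 (25 November 2015)**

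- The last pack-eligible patients enrolled at the end of April 2015. Adding 24 weeks (168 days) gives mid-October 2015, so the 6-, 12- and 24-week packs were already out, barring long admissions.
- 25 November 2015 minus 48 weeks (336 days) is 24 December 2014. Pack-eligible patients discharged from then on still had a 48-week pack to come.
- Two-year questionnaires due between 25 November 2015 and 1 October 2016 belong to patients discharged between 25 November 2013 and 1 October 2014, if selected.

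**The case against.** The strongest reply is that the point is narrow. Recurrence requires CSF pleocytosis and so a hospital lumbar puncture. CSF samples reaching participating laboratories are screened (5.1), so some repeat episodes may surface without the participant calling. The socio-economic questionnaire and the CRF are not reproduced, so one can say only that a readmission question is not described. Fever relapse does not depend on the TMS. Section 13.1.1 speaks of no longer sending the TMS on discharge, which leaves open whether inpatient scoring continued. And by version 7.2 most packs had gone out.

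Much of this stands as a limit on size. But laboratory screening is set up for enrolment and is not assigned as a recurrence check, and an admission elsewhere would escape it. One question covering the whole time since discharge recovers earlier events from a late contact.

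Three stronger readings are tempting and are not supported:

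- **Serious events after discharge are found only if volunteered.** Section 8.5 says otherwise: "The local investigator is responsible for reporting all AEs that are observed or reported during the study, regardless of their relationship to study", and "All other adverse events should be reported on the regular progress/follow-up reports". Section 8.7 allows a site visit when case notes are suspected of holding unreported events. Nor is there an absence of contact after discharge: 6.1, 6.7 and 6.8.3 all provide some.
- **Late enrolees stay in the denominator and dilute the incidence in proportion to their number.** No analysis population is stated for 7.1.2(c), and a statistical analysis plan may set one. Full dilution also needs zero detection in these patients, whereas the request in 6.3.2 still covers them. Since the packs are not described as asking about recurrence, stopping them removes no stated detection route.
- **Reporting differs between diagnostic groups.** This is plausible, but nothing in the protocol shows it, and 6.3.2 defines recurrence for viral meningitis only.

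**Conclusion.** The point holds in two limited parts. First, the only stated detection route for recurrence is passive, while scheduled contacts that could carry the question are not described as doing so. Downward bias in 7.1.2(c) is likely, but its size cannot be derived; the 10% to 50% loss shown rests wholly on an assumed capture of 90% to 50%. Second, for patients enrolled from May 2015, recurrence and headache relapse cannot be assessed after discharge as defined, and fever relapse loses its home data source. That follows directly from 6.3.1.4, 6.3.2, 6.4.6 and 13.1.1 and needs no assumption, apart from the doubt over inpatient scoring.

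This affects secondary outcomes of an observational study, not the primary prevalence estimate. It should be corrected because the remedy is small and the relapse and recurrence figures are otherwise hard to interpret.

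**What to change.** - Add one item to every remaining pack, the one-year call and the two-year questionnaire: whether, since discharge, the patient has been readmitted or had another lumbar puncture, and where and when. Ask it on the call as part of the interview already planned.
- Have the coordinating centre pass each positive answer to the site, which obtains the CSF result and completes any SAE form due.
- Restrict the numerator and denominator of the TMS-dependent outcomes, 7.1.2(b) and (c), to patients enrolled while the TMS and packs were issued. Report recurrence in later enrolees separately, labelled as self-reported only.
- State that patients with no remaining scheduled contact at the time of the change also rest on self-report.

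The cost is one question, an amendment and some site follow-up of positive answers. The denominator falls and the interval widens. If a share f of patients is set aside, the width grows by about 1/√(1 − f): for f = 17/60, 1/√0.717 = 1.18, or 18% wider. For an assumed f of 0.10 to 0.40 it is 5% to 29% wider. The question will not recover events in patients already past their last contact.
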